7.7.3.3 Viral Infection Screen Panel

Data for viral infection screen panel received from central and local laboratory will be listed by treatment group and visit for Safety set with site 065-S .

Hepatitis screening	HIV screening
Hepatitis B antigen (HBsAg) Hepatitis C virus antibody (anti-HCV), in case of positive result, reflex test of HCV circulating Ribonucleic acid (RNA)	Anti-human immunodeficiency virus (HIV) 1 and 2

Statistical Analysis Plan

Sponsor Name: Poxel
Sponsor Protocol ID: PXL065-003

7.7.3.4 Serum and Urine Pregnancy Test

For female patients of child-bearing potential only, a serum B Human Chorionic Gonadotropin (β -HCG) test or a urine pregnancy test will be performed.

Additional serum pregnancy testing should be performed during the study whenever a menstrual cycle is missed or when pregnancy is otherwise suspected.

Serum and Urine pregnancy test results will be summarized for the Safety set.

Serum and Urine pregnancy test results, and immediate pregnancy reporting will be listed for the Safety set with site 065-S: .

7.7.4 Bone Mineral Density

For postmenopausal women only, a standard dual-energy X-ray absorptiometry (DXA) testing will be performed during the study.

If possible, all DXA testing for a given patient (historical testing or testing performed during study) should be performed at the same facility and using the same procedure.

Bone mineral density will be summarized by visit using standard descriptive statistics for each treatment group, changes from baseline will also be summarized. Summary tables will be produced for the Safety set.

Bone mineral density test results will also be listed for the Safety set with site 065-S: .

7.7.5 Vital Signs and Body Measurements

The following vital sign and body measurements will be taken during the study:

- height (cm)
- weight (kg)
- waist circumference (cm)
- hip circumference (cm)
- Waist-to-hip ratio [Derived as waist circumference (cm)/hip circumference (cm)]
- heart rate (bpm)
- SBP (mmHg) with 3 readings
- DBP (mmHg) with 3 readings

The following vital sign results are derived on the eCRF:

- calculated BMI (kg/m^2)
- mean SBP (mmHg)
- mean DBP (mmHg)

Vital signs data and changes from baseline in vital signs will be summarized visit by using standard descriptive statistics for each treatment group the Safety set. For summaries, the average of the 3 blood pressure readings will be used.

Summary table on weight will be repeated in the Safety set with site 065-S: .

Statistical Analysis Plan

Sponsor Name: Poxel
Sponsor Protocol ID: PXL065-003

The MMRM analysis described in Section 7.6.2.3 will be repeated for the Safety set, Safety set with site 065-S and ITTS for weight (kg).

A listing of vital signs data will be produced for the Safety set with site 065-S .

7.7.6 Electrocardiograms

The following quantitative ECG measurements will be taken during the study:

- heart rate (bpm);
- PR interval (msec);
- QRS interval (msec);
- QT interval (msec);
- Fridericia corrected QT (QTcF) interval (msec);

An overall Investigator assessment of ECG will be provided (categories "normal", "abnormal, not clinically significant" and "abnormal, clinically significant"). Any new clinically significant findings or worsening of abnormalities previously recorded as Medical History on the ECG will be reported as AEs, and followed up and/or treated locally until the AE has resolved or the condition has stabilized.

The ECG measurements and changes from baseline in ECG will be listed for the Safety set with site 065-S and summarized by treatment group and visit using standard descriptive statistics for the Safety set.

The Investigator assessment will be listed for the Safety set with site 065-S and the number and percentage of subjects within each assessment category will be tabulated for each treatment group by visit for the Safety set.

Summary tables will be produced for the Safety set.

A listing of ECG measurements and findings will be produced for the Safety set with site 065-S .

7.7.7 Physical Examination

Any new clinically significant abnormal findings or worsening of conditions previously recorded as medical history should be documented in the source documents and reported in the eCRF as AE.

Physical examination date will be listed for the Safety set with site 065-S .

7.7.8 Pitting Edema

Shift tables from baseline will be presented at each post-baseline visit showing the number of patients per treatment group with each populated grade for the Safety set.

A listing will also be provided for the Safety set with site 065-S .

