Pioglitazone was first approved in the United States in 1999 and has been prescribed extensively for the treatment of T2DM. As of 2014, it was estimated that there were over 29 million patient years of exposure data available for pioglitazone [4]. Pioglitazone has been studied in humans as well as animal models for indications other than T2DM, including NASH. The safety profile of pioglitazone has been established via numerous animal toxicology studies, human clinical studies, and through its extensive use as an active ingredient in approved drugs. The efficacy of pioglitazone in both nondiabetic and diabetic NASH patients has been demonstrated in randomized controlled studies [5] and the use of pioglitazone in nondiabetic or diabetic biopsy-proven NASH patients is recommended by the practice guidance of the American Association for the Study of Liver Diseases (AASLD) [6] and of the European Association for the Study of the Liver [7]. However, in the United States, pioglitazone is prescribed by only about 14% of gastroenterologists and hepatologists to their biopsy-proven NASH patients, due primarily to its propensity to induce weight gain [8, 9].

Pioglitazone is a member of the class of compounds known as thiazolidinediones (TZDs). TZDs are known to be PPAR $\gamma$  activators. However, while PPAR $\gamma$  activation has been shown to result in positive pharmacological effects, PPAR $\gamma$  activation can also explain many of the side-effects observed in patients treated with TZDs. Specifically, PPAR $\gamma$  activation has been linked to weight gain [10], fluid retention [11], and bone loss [12, 13]. Recently, pioglitazone and other TZDs have been reported to exert pharmacological activity through additional, non-PPAR $\gamma$ -related mechanisms of action including

inhibition of mitochondrial pyruvate carrier (MPC) [14]. MPC inhibition, as opposed to PPAR $\gamma$  activation, is predicted to provide the treatment benefits for NASH patients [15].

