### 8.3.2 Pitting edema assessment

At each visit, an assessment of pitting edema will be performed.

The pitting edema will be assessed following this procedure:

- Place your index finger over the patient's tibia, 10 cm above the lateral malleolus
- Exert pressure for 5 seconds
- Any depression that does not resume its original contour almost immediately is a sign of pitting edema

If the presence of pitting edema is confirmed, the following scale should be used to grade it.

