**Table 3. Pitting edema scale**

Grade	Physical Characteristics
1+	No visible change in shape of the extremity

	Pitting $\leq$ 2 mm Pit disappears rapidly
2+	No marked change in the shape of the extremity 2 mm $<$ pitting $\leq$ 5 mm Pit usually disappears in 10-15 seconds
3+	Noticeable swollen extremity 5 mm $<$ pitting $\leq$ 10 mm Pit may persist for about a minute
4+	Very swollen and distorted extremity Very deep pit $>$ 10 mm Pit may persist 2 – 5 minutes

The presence or absence of edema will be recorded at each visit (Yes/No). If there is a pitting edema, a grade will be recorded for the edema according to the pitting edema scale.

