#### *9.5.3.3 Physical Examination, Pitting Edema, Vital signs and Body measurements, Bone mineral density and ECG*

Physical examination, pitting edema assessment, vital signs and body measurements, bone mineral density and ECG parameters will be summarized descriptively by treatment and timepoint. Similarly, changes from baseline will be summarized.

Physical examination results will be listed by patients and body system.

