6.1 Time Points and Visit Windows

Day 1 is defined as the day of randomization. Relative days after Day 1 are calculated as (assessment date – Day 1 date) + 1. Relative days prior to Day 1 are calculated as (assessment date – Day 1 date). The day prior to Day 1 is Day -1.

To maximize the data available for analysis, where possible, results from ET and Unscheduled Visits will be allocated to scheduled visit according to the following rules and visit windows described in Table 2.

- If a valid value exists for the scheduled visit to which the ET/Unscheduled Visit has been allocated then the value from the scheduled visit will be used in the analysis, otherwise the values from the ET/Unscheduled Visits will be used in the analysis for the particular scheduled visit.
- If more than one ET/Unscheduled Visit is allocated to the same scheduled visit (and no valid value from the scheduled visit is available) then the closest visit value will be used in the analysis for the scheduled visit.

Visit Windowing rules are defined according to parameters groups in **Table 1** - **Visit window groups** and the windows in **Table 2**.

Double-blind treatment period is defined as the period between the randomization visit (V1) and the EoT visit (V8). Follow-up period is defined as the period between the EoT visit (V8) and the EoS visit (V9).

Table 1 - Visit window groups

Visit window group	Visits	Parameters
Group 1	All visits	Pitting edema assessment, vital signs and body measurements, physical examination
Group 2	Screening, V1, V4, V6, V8	HbA1c
Group 3	Screening, V1, V4, V6, V8, V9	Safety lab, FPG
Group 4	Screening, V1, V5, V8, V9	ECG
Group 5	Screening, V8	DXA, MRI-PDFF, Liver biopsy
Group 6	Screening, V1, V8	eGFR
Group 7	Screening, V1, V5, V9	Pregnancy test
Group 8	V1, V4, V6, V8	Measured metabolic parameters, insulin resistance indexes
Group 9	V1, V8	Fibrosis biomarkers, biobanking sampling

Statistical Analysis Plan

Sponsor Name: Poxel
Sponsor Protocol ID: PXL065-003

Table 2 - Visit windows

Visits	Study day ^a	Group 1	Group 2	Group 3	Group 4	Group 5	Group 6	Group 7	Group 8	Group 9
Screening	N/A	-∞ to -1	-∞ to -1	-∞ to -1	-∞ to -1	-∞ to -1	-∞ to -1	-∞ to -1		
Randomization	1	1 to 12	1 to 43	1 to 43	1 to 64		1 to 127	1 to 64	1 to 43	1 to 127
Week 3	22	13 to 33								
Week 6	43	34 to 64								
Week 12	85	65 to 106	44 to 127	44 to 127					44 to 127	
Week 18	127	107 to 148			65 to 190			65 to 197		
Week 24	169	149 to 190	128 to 211	128 to 211					128 to 211	

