7.1 General Principles

All data processing, summarization and analyses will be performed using SAS Environment / Version 9.4 (or later) of the SAS® statistical software package.

The following principles will be applied to all tables, figures and listings (TFLs) unless otherwise stated:

Principle	Value
Significant tests	Two-sided and use a 5% significance level for main effect
Treatment group labels and order presented	PXL065 7.5mg QD PXL065 15 mg QD PXL065 22.5mg QD Placebo
Visit labels presented	Tables and Figures: Week XX Listings: Screening Randomization (V1) Week 3 (V2) Week 6 (V3) ... Week 36 (V8-EoT) End of Study (V9-EoS) Early termination Unscheduled
Tables	Data in summary tables presented by treatment group, assessment (where applicable) and analysis visit (where applicable).
Listings	All data collected presented by treatment group, patient, nominal visit, Date unless otherwise specified.
Descriptive summary statistics for continuous variables	Number of patients/observations (N) Mean SD standard error of the mean (SEM), median interquartile range (25 th percentile, 75 th percentile) (Q1, Q3) minimum and maximum
Descriptive summary statistics for categorical variables	Frequency counts and percentages: n (%)
Denominator for percentages	Number of patients in the analysis population, unless stated otherwise in table shell(s).
Include "Missing" as category	Yes, when the number missing is greater than zero for at least one treatment group.

Statistical Analysis Plan

Sponsor Name: Poxel
Sponsor Protocol ID: PXL065-003

Principle	Value
Display for 0 percentages	Leave blank
Display to one more decimal place than collected value	Mean SEM Mean Difference Median Interquartile range (Q1, Q3)
Display to 2 more decimal places than collected value	SD Confidence Intervals (CI)
Limit of precision for displays	3 decimal places
Date Format for the presentation in the listings	DDMMYYYY

The baseline value is defined as last scheduled or unscheduled value collected prior to the first dose of IMP treatment, scheduled on Randomization Visit (V1). Assessments carried out on day of first treatment administration are considered to have taken place before the IMP administration, if the corresponding times have not been recorded.

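### Measured pitting edema is tabulated only visit by visit; the SAP plans no per-patient count or worst grade on the 1+ to 4+ scale

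*SAP*

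**What the plan says.** Protocol 8.3.2 has the sign examined throughout: "At each visit, an assessment of pitting edema will be performed". Presence or absence is recorded as Yes or No each time. Table 3 of that section grades edema from 1+ to 4+ and has no grade for absence: "If there is a pitting edema, a grade will be recorded for the edema according to the pitting edema scale".

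For the analysis, protocol 9.5.3.3 plans that "pitting edema assessment, vital signs and body measurements, bone mineral density and ECG parameters will be summarized descriptively by treatment and timepoint". SAP 7.7.8 makes this specific: "Shift tables from baseline will be presented at each post-baseline visit showing the number of patients per treatment group with each populated grade". It uses the Safety set and adds a patient listing. Neither document defines a worst post-baseline grade or an any-time count for the measured scale.

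SAP 6.1 says that, where possible, "results from ET and Unscheduled Visits will be allocated to scheduled visit" windows. If the scheduled visit already has a valid value, that value is used instead.

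Pitting edema is also an AESI (protocol 8.3.8.1.4). SAP 7.7.2 counts each patient with a treatment-emergent AESI once in its overview table, naming pitting edema, and tabulates AESIs by system organ class and preferred term.

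**The concern.** Protocol 2.1 names fluid retention among the effects linked to PPARγ activation, and the case for PXL065 is similar or better efficacy than pioglitazone with fewer side effects. Pitting edema is the graded, protocol-scheduled examination for that effect.

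A shift table at one visit shows who has edema at that visit compared with baseline. It does not show whether the patients in the Week 12 table are those in the Week 6 table. A patient with edema at only one or two visits is never counted once, across the study, as having had new or worse edema. If episodes are short and spread over time, a dose-related excess could appear as one or two patients in each of eight tables, and readers would have no planned cumulative figure on the measured scale to set beside it.

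**Working it through.** **1. Number of tables.** Pitting edema is in visit-window Group 1 of SAP Table 1 (all visits). The post-baseline visits are Weeks 3, 6, 12, 18, 24, 30, 36 and 38: eight in all, seven on treatment and one in follow-up.

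**2. What each planned output gives.**

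| Output | Measured 1+ to 4+ scale | Any-time patient count |
|---|---|---|
| Shift tables (SAP 7.7.8) | Yes | No, one visit at a time |
| Listing (SAP 7.7.8) | Yes | Only if derived by hand |
| AESI overview and AESI by term (SAP 7.7.2) | No, severity is CTCAE | Yes, for events reported as AEs |

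No planned table has both properties.

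**3. Can the any-time count be recovered from the visit tables?** The documents give no edema rate, so this step assumes one. Take 30 patients per arm (the planned randomized number; the Safety set may be smaller) and 3 of 30 with edema at each of the eight visits.

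- Same patients every time: 3/30 = 10% ever affected.
- Independent visits: 1 − (1 − 0.10)^8 = 0.57, or 57%.
- Different patients every time: 8 × 3 = 24, and 24/30 = 80%.

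Identical visit counts therefore fit anything from 10% to 80%. At 5% per visit the range is 5% to 40%; at 15% it is 15% to 100%. The count cannot be recovered.

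**4. How far could one visit table understate it?** Assume 20% of 30 patients are ever affected (6 patients), each with edema visible at k of 8 visits. The average count per table is 30 × incidence × k / 8.

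| Ever affected | k = 1 | k = 2 |
|---|---|---|
| 10% (3 patients) | 3 × 1/8 = 0.375 | 3 × 2/8 = 0.75 |
| 20% (6 patients) | 6 × 1/8 = 0.75 | 6 × 2/8 = 1.5 |
| 30% (9 patients) | 9 × 1/8 = 1.125 | 9 × 2/8 = 2.25 |

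With 6 affected and random onset, simulation puts the fullest single table at about 2.2 patients (k = 1) or 3.2 (k = 2). If instead edema persists once it appears and the patients stay in the study, the Week 36 table shows all 6, and the ratio is 6/6 = 1. The documents do not say which pattern to expect.

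**5. Grades that do not reach the tables.** SAP Table 2 gives Group 1 a Week 12 window of Days 65 to 106. Suppose a patient has no edema at the scheduled Week 12 visit on Day 85, stops IMP, and has 2+ edema at an ET visit on Day 100. The ET grade falls in the Week 12 window, the Day 85 value is valid, and so the 2+ is not used. It appears only in the listing. Likewise, an unscheduled finding on Days 2 to 12 maps to the Randomization window (Days 1 to 12) and so enters no post-baseline table.

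**The case against.** The strongest reply is that an any-time incidence per arm is already planned. Pitting edema is an AESI whether or not it is serious. Signs of heart failure trigger only the cardiology referral, not AESI status. The protocol's AE definition covers any unfavorable sign, and the AESI overview counts patients once. This stands, and it means the trial will not lack a cumulative edema figure altogether. It does not fully replace the measured scale. Protocol 8.3.2 contains no instruction to report a finding as an AE, and the physical examination rule in 8.3.1 asks for new clinically significant findings or worsening, which is a judgment. AE severity is CTCAE, not 1+ to 4+.

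A second reply is that safety is declared descriptive in a Phase 2 trial for internal decision, and that protocol 4.2 looks to weight to confirm reduced PPARγ activity. SAP 7.7.5 gives weight a repeated-measures model, with differences from placebo. This also stands. It lowers the weight of the point and makes a confidence interval for edema optional.

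A reader might also infer three stronger claims that the documents do not support:

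- **That edema cannot be compared between arms.** The shift tables are by treatment group, so arms can be compared at every visit.
- **That edema-free and unassessed patients are pooled.** SAP 7.1 adds a Missing category ("Yes, when the number missing is greater than zero for at least one treatment group"), but nothing there treats a recorded No as missing. Pooling is a possible reading of a section that does not say how absence enters the table. The table shells, which are not in these documents, may settle it.
- **That ECG needs the same repair.** SAP 7.7.6 does say that "the number and percentage of subjects within each assessment category will be tabulated for each treatment group by visit", without crossing with baseline. But new clinically significant or worsened ECG findings are reported as AEs, and changes from baseline in the ECG measurements are summarized.

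**Conclusion.** The point holds as a reporting gap. The planned tables give visit-level comparisons of measured edema but no per-patient cumulative count and no worst grade, and the window rule can leave out ET and unscheduled grades. The AESI tables fill part of the gap, subject to investigator reporting and a different grading scale.

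The size is unknown. A reader might infer a large understatement, such as 8-fold from 6/0.75, but that needs every episode to be visible at only one of eight visits, and the documents give no basis for that. With persistent edema the understatement is about 1-fold. The incidence figures are assumptions. The any-time count could still be derived from the listing, but the definition would then be chosen after the data are seen. No efficacy result, error rate or sample size is affected. This is an inexpensive improvement, not a flaw that threatens the trial's conclusions.

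**What to change.** In SAP 7.7.8:

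1. Use the recorded Yes/No to show absent edema as its own category in every shift table, separate from not assessed.
2. Add one shift table, by arm, from baseline to the worst on-treatment grade, taking all scheduled, ET and unscheduled post-baseline assessments without the one-value-per-window rule of SAP 6.1. State the cut-off for on-treatment so that the ET visit, due within 8 days after IMP discontinuation, is clearly in or out.
3. Under that table give n (%) of patients per arm with an increase of at least one grade, counting absent to 1+ as one grade. A descriptive difference from placebo with a 95% CI is optional.

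The by-visit tables can stay as they are apart from item 1. The cost is one extra descriptive table and a few lines of SAP text. The data are already collected, and no new assessment or protocol amendment is needed.

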7.7.9 Other Safety Variables

Blood (total, plasma and serum) samples for supplementary tests will be collected at particular visits to enable post-hoc testing of any additional efficacy and safety parameters or any potential biomarkers related to liver, cardiovascular diseases or metabolic diseases in relation with the drug target. The samples will be stored until

Statistical Analysis Plan

Sponsor Name: Poxel
Sponsor Protocol ID: PXL065-003

further use. All the biobanking samples will be destroyed within 2 years after the final study report is issued.

7.8 Interim Analysis

Not applicable

8. Changes in Planned Analysis

- Changes from SAP v2.0 (12May2022) to SAP Final v3.0 (12Aug2022):
 - Treatment exposure end date coded as 23rd December 2021 per NTF for patients that did not complete the study at site 065-S
 - PPS description updated following the BDRM
 - Removal of analyses utilizing multiple imputation on the PPS
 - Multiple imputation method updated to consider a minimum and maximum value
 - CMH and logistic regression analysis removed for “Patients without any MRI assessments on treatment being classified as non-responders”
 - Analysis on biopsy exploratory endpoints updated to consider only patients with Week 36 assessments
 - EoS Visit end date removed for derivation of new medications
- Changes from SAP v1.0 (03Dec2020) to SAP Final v2.0 (17May2022):
 - Updates per issue with site 065-S
 - Section 1 updated to mention note to file for the handling of site 065-S
 - Analysis populations section includes description of the issue with site 065-S and the handling of the analysis sets
 - Section 7 updated to specify which analyses are done with and without site 065-S
 - Updates to disposition table
 - Additional MMRM analysis for weight (kg)
 - Section 7.6.2.5 added for new subgroup analyses on secondary endpoints
 - Updates per dry run 1
 - Rescreened patients excluded from screened set
 - Demographics - BMI and Weight at baseline rather than randomization
 - Updates to TEAE overall table
 - Inclusion of urine pregnancy summary and listing
 - Inclusion of immediate pregnancy reporting listing
 - Updates per protocol amendment 5
 - Additional section for handling of rescreened patients
 - Removal of albuminuria/creatininuria ratio
 - Updates to prohibited medication
 - Imputation rules added for type 2 diabetes diagnosis
 - PK analysis is now being reported separately

Statistical Analysis Plan

Sponsor Name: Poxel
Sponsor Protocol ID: PXL065-003

- References to Covance updated to Labcorp/Labcorp Drug Development
- Approval of SAP version 1.0 dated 03Dec2020

9. Data Issues

Issues concerning site 065-S have been documented in Section 5 and in a note to file.

10. References

- 1 ICH. *Statistical Principles for Clinical Trials*, Guideline E9, 1998. Available at <http://www.emea.eu.int/pdfs/human/ich/036396en.pdf>
- 2 CPMP. *Points to Consider on Missing Data*. EMEA: London, 2001. Available at <http://www.emea.eu.int/pdfs/human/ewp/177699EN.pdf>
